1.2. Study Design

Study 64281802DNG2004 (further referred to as DNG2004) is Phase 2 randomized, double-blind, placebo-controlled, double-dummy, multicenter, interventional trial with an event-driven design that will evaluate the prophylactic efficacy (PE) and safety of 2 dose regimens of JNJ-64281802 for the prevention of dengue infection in HHCs of a DENV-infected index case.

As there can be up to 4 DENV serotypes circulating at any time in dengue-endemic regions, the conduct of the study in dengue-naïve as well as in dengue-post exposed study participants in endemic regions allows for the assessment of the efficacy of the 2 dose regimens and of the ultimate decision on one dose selection.

[figure not shown]
There are 4 sequential phases in the study: DENV-infected index case identification, screening of the household contacts (HHCs) of the index case, double-blind prophylactic dosing, and the follow-up phase.

The study included index cases ≥ 1 years of age who participated for one visit only, and HHCs aged 16 or 18 (depending on the legal age of consent in the jurisdiction in which the study is taking place) to ≤ 65 years who were included in the intervention part of the study.

An index case is a patient (≥1 years old) with laboratory-confirmed dengue identified in the community (ie, hospital and/or health care center/health care provider). If the index case was a minor according to the local laws and regulations, assent and informed consent from the parent(s) or legal guardian(s) or legally acceptable representative(s) was obtained. After informed consent/assent was obtained from the patient or from the legal guardian(s), a blood sample for viral assessments was collected, and the person's HHCs were contacted.

A HHC is a person who lives, spends the night, or regularly attends/shares/consumes cooking/meals in the same dwelling or housing complex as the index case. A household can include one or more families, or community contacts in a single or in multiple houses or dwellings, depending on the country, site, social-economic, and cultural characteristics. Co-workers and acquaintances can also be considered HHCs, if they spend time together with the index case (eg, during early morning hours or twilight hours). HHCs had to be asymptomatic at screening and could include participants with no evidence of current DENV infection (consisting of naïve and historical DENV infected participants) or with evidence of current DENV infection as confirmed by laboratory assessments on samples taken at baseline.

Participants (ie. HHCs) were randomized in a 1:1:1 ratio to receive the study intervention as high dose regimen (HDR), low dose regimen (LDR), or as matching placebo in a double-dummy fashion. The study used randomization at the individual participant level. Participants were assigned to 1 of 3 intervention groups based on a computer-generated randomization schedule prepared before the study by or under the supervision of the sponsor. The randomization was balanced by using randomly permuted blocks and was stratified by country. A separate randomization list was created for the PK substudy.

- * Based on negative results for DENV RNA and NS1 protein assays
- ° Based on positive results for DENV RNA or NS1 protein assays

The interactive web response system (IWRS) assigned a unique intervention code, which dictated the intervention assignment and matching study intervention kit for the participant. The investigator will not be provided with randomization codes. The codes will be maintained within the IWRS, which has the functionality to allow the investigator to break the blind for an individual participant.

Data that may potentially unblind the intervention assignment (ie, study intervention serum concentrations, virologic data, study intervention preparation/accountability data, intervention allocation, biomarker, or other specific laboratory data) will be handled with special care to ensure that the integrity of the blind is maintained and the potential for bias is minimized. This can include making special provisions, such as segregating the data in question from view by the investigators, clinical team, or others as appropriate until the time of database lock and unblinding.

The primary hypothesis of this study is that JNJ-64281802 is superior to placebo with respect to prevention of laboratory-confirmed DENV infection (further referred to as DENV infection) from baseline until the last day of dosing + 1 day in study participants who are DENV RNA and NS1 protein negative at baseline (further referred to as the primary analysis population). DENV infection will be measured by a positive result on a DENV RNA assay and/or a DENV NS1 protein assay.

The study is an event-driven design where study recruitment was planned until the required number of events was reached. The study consists of 2 stages with an IA at the end of Stage 1 and the FA at the end of Stage 2 (ie, the end of the study). The objective of Stage 1 was to obtain proof-of-concept (PoC) on the primary hypothesis. The objectives of Stage 2 were to select the dose for future development and to confirm superiority of the selected dose above placebo.

The IA was scheduled when 24 DENV infections were observed in the primary analysis population. All HHCs with an enrollment date before or at the date of this 24th laboratory confirmed DENV infection would be included in the IA. The IA data base should have been

cleaned and locked and should have contained all data of the included HHCs that is needed to derive the primary endpoint, all PK data and all safety and tolerability data up to their last day of dosing (day 28 or earlier, in case of discontinuation) + 1 day.

Based on the results from the IA and other available information from other studies (eg, human challenge), the LDR could be dropped in Stage 2.

Unless stopped for futility at the IA, the study would continue till 36 DENV infections were observed in the primary study population and 24 symptomatic DENV infections were observed in the complete study population. Symptomatic DENV infections are defined as having at least 2 solicited systemic AEs (see protocol 1), of which at least one is a most common dengue symptom (ie, fever, headache/retro-orbital pain, myalgia, arthralgia, rash), lasting for ≥ 1 day and occurring within a ± 1 -2 days' time window around the positive PCR or NS1 test, between baseline and the last day of dosing ± 1 day. Both conditions on DENV infections and symptomatic DENV infections needed to be satisfied before recruitment was considered complete.

The study was prematurely ended before the IA on 02 October 2024 due to portfolio reprioritization., therefore no IA is performed and the analysis after this premature end will be considered as FA. This decision was not based on any safety concerns.

2. STATISTICAL HYPOTHESES

The primary hypothesis of this study is that JNJ-64281802 is superior to placebo with respect to prevention of laboratory-confirmed DENV infection from baseline until the last day of dosing + 1 day in study participants who are DENV RNA and NS1 protein negative at baseline.

Laboratory-confirmed DENV infection is defined as a positive DENV RNA or a DENV NS1 protein (ELISA) test result. The primary efficacy endpoint is the presence or absence of a laboratory-confirmed DENV infection between baseline and the last day of dosing + 1 day. The primary analysis population consists of study participants who are DENV RNA and NS1 protein negative at baseline. The null hypothesis is that the DENV infection rate from baseline until the last day of dosing + 1 day in the primary analysis population is at least as high in participants on prophylactic dosing with JNJ-64281802 than in participants on placebo.

3. SAMPLE SIZE DETERMINATION

The study is an event-driven design where study recruitment would continue until the required number of events was reached. Unless stopped for futility at the IA, the study would continue till 36 DENV infections were observed in the primary study population and 24 symptomatic DENV infections were observed in the complete study population (see Section 4, Populations for Analysis). Both conditions needed to be satisfied before recruitment could be considered complete. An IA for PoC was planned when 24 DENV infections were observed in the primary study population. The targets of 24/36 DENV infection events in the primary study population and 24 symptomatic DENV in the complete study population were determined through simulation based on the following requirements and assumptions.

Requirements

- at the IA 90% power is required, using a 20% one-sided significance level, to obtain PoC on the primary endpoint (DENV infections in the primary study population) for HDR and LDR if they reach the target PE of 75%;
- at the FA 80% power is required, using a 2.5% one-sided significance level, to test the primary hypothesis of the study for HDR and LDR if they reach the target PE of 75%;
- in addition, at the FA, 80% power is required, using a 20% one-sided significance level, for PoC for the key secondary endpoint (symptomatic DENV infections in the complete study population) if at least HDR reaches the target PE against symptomatic DENV infection of 72.5%;

Assumptions

- the number of eligible and recruited HHC per index case was hypothesized to be 1.5;
- the proportion of unevaluable subjects (drop-outs, missing data) was hypothesized to be 20%;
- the proportion of recruited HHC NS1+ and/or PCR+ at recruitment was hypothesized to be 20%;
- the incidence of DENV infection events in the primary study population was hypothesized to be 7.5% during the 28-day dosing period. This assumption is based on the 15 to 18% incidence of DENV infection in Nha Thrang (unpublished data), Vietnam, as observed during an epidemiologic study of HHCs using seroconversion over a 1-month period after identification of the index case. An incidence of ~50% of the observed seroconversion rate was assumed to cover variations in incidence rates across sites and countries and to allow for potential false positive seroconversion results;
- the proportion of incident DENV infections that become symptomatic in the primary study population was hypothesized to be 20% during the 28-day dosing period;
- the proportion of prevalent DENV infections that become symptomatic in the secondary study population was hypothesized to be 10% during the 28-day dosing period.

The simulations are fully described in the modelling and simulation report (MSR)², which also contains the simulation programs.

The simulations showed that at the FA and under the protocol assumptions, the study design results in at least 85% power for the primary objective assessed for the HDR and at least 80% power for the key secondary analysis, irrespective of the PE LDR. If the PE LDR is at least 90% of the PE HDR, the study also has at least 80% power for the primary objective assessed for the LDR and has at least 90% power for the key secondary objective. The expected recruitment of the study ranges from 1250 (assuming the PE of LDR is 0%) to 1850 (assuming the PE of LDR is equal to the PE of HDR, ie. 75%). If the PE of LDR is 50% of the PE of HDR, the expected study recruitment is 1455. If 1.5 eligible HHC can be recruited/index case, this requires the identification of nearly 1000 index cases

The study design is robust to minor deviations from the protocol assumption. If the PE of HDR is 5 percentage points lower than the protocol assumptions, the power for the primary analysis (HDR) is maintained to \geq 77%. If the incidence or prevalence of (symptomatic) DENV infections is different from protocol assumptions, the proposed design generally maintains a power for the primary analysis \geq 80% and for the key secondary analysis \geq 75%. However, if incidence of (symptomatic) DENV infections is lower than expected the total study recruitment will be increased.

The study ended prematurely when 21 laboratory confirmed dengue infections between baseline and last day of dosing (+1 day) were observed in the primary analysis population and 14 symptomatic dengue infection between baseline and last day of dosing (+1 day) were observed in the completed study population.

4. POPULATIONS (ANALYSIS SETS) FOR ANALYSIS

For purposes of analysis, the following populations are defined:

Population	Description				
Enrolled	All participants (index cases and HHCs) who sign the ICF.				
Index Case	All participants enrolled as an index case, with a laboratory-confirmed DENV infection.				
population					
	Test results of a NS1 rapid test and/or RT-PCR test that were performed outside the study by				
	local standard-of care ≤72 hours of screening may be used to confirm the DENV infection.				
Randomized	All participants (HHCs) who are randomized in the study.				
Safety	All randomized participants who received at least one dose of study intervention.				
	This population will be used for the safety analysis.				
Primary study	All randomized participants who received at least one dose of study intervention, who had no				
population	evidence of current DENV infection at baseline (based on target not detected (TND) results for				
	DENV RNA assay and, if available, a negative/borderline result for NS1 protein assays) and				
	with at least 1 result for DENV RNA or NS1 protein assay available post baseline up to and				
	including the last day of dosing + 1 day				
	This population will be used for the primary, secondary, and exploratory efficacy analyses.				
Secondary study	All randomized participants who received at least one dose of study intervention, who had				
population	evidence of current DENV infection (based on positive results for DENV RNA or NS1 protein				
	assays at baseline) but without DENV signs and symptoms at baseline.				
	This population will be used to evaluate the exploratory objective of an antiviral effect of JNJ-				
	64281802 as early treatment.				
Complete study population	All participants included in the primary or secondary study population.				
1 1	This population will be used to investigate the key secondary endpoint of the effect of				
	JNJ-64281802 on the prevention of symptomatic DENV infection.				
PK	All participants who received at least one dose of study intervention and who have at least one				
	plasma concentration data value after dosing.				
	This population will be used to the assess the plasma concentrations of JNJ-64281802.				

 $CONFIDENTIAL-FOIA\ Exemptions\ Apply\ in\ U.S.$

5. STATISTICAL ANALYSES

5.1. General Considerations

All analysis dataset preparations and statistical analyses will be performed using SAS® version 9.4 or higher. Figures can be generated in R.

Index cases participated for one visit only, therefore the next sections are only applicable to the HHCs. Descriptive statistics that will be provided for the index cases can be found in Appendix 3, Index Cases.

5.1.1. Analysis Phase Definition

The Prophylactic Dosing phase used for the safety evaluation and as defined below is extended compared to the Prophylactic Dosing phase as defined in the protocol considering the long half-life (~10 days) of the study intervention.

Following analysis phases are defined:

Table 1: Construction of analysis phases

Analysis phase Start date		End date		
Screening	The date &	& time of signing the 1 minute before date & time of first study drug intake**.		
(phase 1)	informed cor	nsent*		
Prophylactic	DosingDate & time	of first study drug intake**	Minimum of:	
(phase 2)	(JNJ - 64281	802 or Placebo)	a. Date of Day 50 Visit at 23.59h***	
			b. Date of study termination at 23.59h	
Follow-up	End of the P	rophylactic Dosing phase	Study termination date (date of last contact) at 23.59h	
(phase 3) ***	+1 minute			

^{*:} if no time is available then impute with 00:00

5.1.2. Visit Windows

As participants do not always adhere to the protocol visit schedule, the following rules are applied to assign actual visits to analysis visits. Listed below are the visit windows and the target days for each visit. The reference day is the date of first study intervention intake. The relative day (reldy) of each visit will be defined as:

- reldy = visit date reference date + 1 for visits on or after Day 1,
- reldy= visit date reference date for visits before Day 1.

Consequently, there is no 'Day 0' defined.

If a participant has 2 or more actual visits in 1 visit window, the visit closest to the target day will be used as the protocol visit for that visit window. The other additional visit(s) will not be used in the summaries or analyses, but they can be used for determination of clinically important endpoints. If 2 actual visits are equidistant from the target day within a visit window, the later visit is used.

^{**} If no time is available and randomization happened on the same day, then impute with randomization time.

^{***} If no Day 50 Visit was performed, the date of first study intervention intake + 49 days will be used. Participants recruited under protocol version 1 (dd. 09NOV2021) or earlier will not have a Follow-up phase and will have their prophylactic phase ending at Study termination date (date of last contact) at 23:59h.

All assignments will be made in chronological order. Once a visit date is assigned to a visit window, it will no longer be used for a later time point. Listed below (Table 2]) are the analysis visit windows and the target days for each visit defined in the protocol.

Table 2: Visit Windows

Parameter	Analysis Phase	Scheduled Visit Number	Time Interval (label on output)	Time Interval (Day)*	Target Time Point (Day)
[Antiviral	[Screening]	[2]	[Baseline]	[<= 1]	[1]
Activity/	[Prophylactic]	[6]	[Day 5]	[1 to 7]	[5]
Immune]	[Prophylactic]	[10]	[Day 9]	[8 to 11]	[9]
	[Prophylactic]	[14]	[Day 13]	[12 to 15]	[13]
	[Prophylactic]	[18]	[Day 17]	[16 to 19]	[17]
	[Prophylactic]	[22]	[Day 21]	[20 to 23]	[21]
	[Prophylactic]	[26]	[Day 25]	[24 to 26]	[25]
	[Prophylactic]	[29]	[Day 28]	[27 to 34]	[28]
	[Prophylactic]	[30]	[Day 40]	[35 to 45]	[40]
	[Prophylactic]	[31]	[Day 50]	> 45	[50]
	[Follow-up]	[35]	[Day 90]	>45	[90]
[Clinical	[Screening]	[2]	[Baseline]	[<= 1]	[1]
Laboratory]	[Prophylactic]	-	[Unscheduled]	[1 to 11]	-
	[Prophylactic]	[14]	[Day 13]	[12 to 15]	[13]
	[Prophylactic]	-	[Unscheduled]	[16 to 26]	-
	[Prophylactic]	[29]	[Day 28]	[27 to 34]	[28]
	[Prophylactic]	-	[Unscheduled]	[35 to 45]	-
	[Prophylactic]	[31]	[Day 50]	> 45	[50]
[Vital Signs]	[Screening]	[1]	[Baseline]	[<= 1]	[1]
	[Prophylactic]	-	[Unscheduled]	[1 to 26]	-
	[Prophylactic]	[29]	[Day 28]	[27 to 34]	[28]
	[Prophylactic]		[Unscheduled]	[35 to 45]	
	[Prophylactic]	[31]	[Day 50]	> 45	[50]
[ECG]	[Screening]	[1]	[Baseline]**	[<= 1]	[1]
-	[Prophylactic]	[4]/-	[Day 3]/[Unscheduled]#	[1,5]	[3]
	[Prophylactic]	-	[Unscheduled]	[6 to 15]	-
	[Prophylactic]	[29]	[Day 28]	[27 to 34]	[28]
	[Prophylactic]	-	[Unscheduled]	>34	-
[Physical	[Screening]	[1]	[Baseline]	[<= 1]	[1]
examination]	[Prophylactic]	-	[Unscheduled]	[1 to 44]	-
	[Prophylactic]	[31]	[Day 50]	> 45	[50]
[PK]	[Screening]	[1]	[Baseline]	[<= 1]	[1]
	[Prophylactic]	[4]	[Day 3]	[3]	[3]
	[Prophylactic]	[6]	[Day 5]	[4 to 6]	[5]
	[Prophylactic]	=	[Unscheduled]	[7]	=
	[Prophylactic]	[10]	[Day 9]	[8 to 10]	[9]
	[Prophylactic]	-	[Unscheduled]	[11]	-
	[Prophylactic]	[14]	[Day 13]	[12 to 14]	[13]
	[Prophylactic]	-	[Unscheduled]	[15 to 19]	-
	[Prophylactic]	[22]	[Day 21]	[20 to 22]	[21]
	[Prophylactic]	-	[Unscheduled]	[23 to 26]	-
	[Prophylactic]	[29]	[Day 28]	[27 to 29]	[28]
	[Prophylactic]	-	[Unscheduled]	[30 to 37]	-
	[Prophylactic]	[30]	[Day 40]	[38 to 42]	[40]
	[Prophylactic]	-	[Unscheduled]	[43 to 47]	-
	[Prophylactic]	[31]	[Day 50]	[48 to 52]	[50]
	[Prophylactic]	-	[Unscheduled]	[53 to 87]	-

CONFIDENTIAL – FOIA Exemptions Apply in U.S.

Parameter	Analysis Phase	Scheduled Visit Number	Time Interval (label on output)	Time Interval (Day)*	Target Time Point (Day)
	[Follow-up]	[35]	[Day 90]	[88,92]	[90]

^{*} Relative to date of first study drug intake

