1.3.2.4. Discontinuation From Study Intervention or Study

Visit Day	Withdrawal Visit ^a	Follow-up Visit ^a	
Visit Window			
Study Procedure			Notes
Study Visit / Contact			
On-site visit or visit at home ^b	X	X	
Return of diary and thermometer	X		
Study Intervention Administration			
Return of study intervention	X		At the withdrawal visit, all study intervention dispensed to the participant should be returned to the site.
Accountability of study intervention	X		
Antiviral Activity Assessments			
Blood sample collection for DENV VL determination (RT-qPCR, NS1 testing) ^c	X	X	
Immune Assessments			
Blood sample collection for humoral immunity (IgG and IgM) ^c	X	X	
Blood sample collection for humoral immunity (nAb) ^c	X	X	
Viral Genome Sequencing			
Blood sample collection for viral genome sequencing	X	X	Viral sequencing will only be performed on DENV RNA positive samples.
Safety Assessments ^d			
Physical examination	X		The physical examination includes a review of the following systems: head/neck/thyroid, eyes/ears/nose/throat, respiratory, cardiovascular, lymph nodes, abdomen, skin, musculoskeletal, and neurological.
Vital signs ^c	X	X	Systolic and diastolic blood pressure and pulse/heart rate (supine after ≥5 minutes rest).
Body temperature	X		Body temperature is to be measured orally in the absence of antipyretic medication, or at least 4 hours after the last intake of antipyretic medication (if applicable) and will be assessed by study site personnel.
12-lead ECG ^c	X	X	Should be performed after ≥ 5 minutes rest in supine position.
Urine pregnancy test ^f	X		For all women.
Clinical Laboratory Tests ^d			
Blood sample collection for hematology ^c	X	X	
Blood sample collection for serum chemistry ^c	X	X	

Visit Day	Withdrawal	Follow-up Visita	
	Visit ^a		
Visit Window			
Study Procedure			Notes
Blood sample collection for coagulation ^c	X	X	
Pharmacokinetics			
Blood sample collection for PK ^c	X	X	
Biomarkers			
Blood sample collection for host RNA assessments ^c	X	X	
Blood sample collection for exploratory biomarker research ^c	X	X	
Ongoing Participant Review ^e			
Concomitant therapy	X	X	Will be collected by study site personnel.
AEs	X	X	Will be collected by study site personnel.

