AE = adverse event; DENV = dengue virus; ECG = electrocardiogram; HHC = household contact; ICF = informed consent form; Ig = immunoglobulin; nAb = neutralizing antibody; NS = nonstructural protein; PK = pharmacokinetic(s); RT-qPCR = quantitative reverse transcription polymerase chain reaction; RNA = ribonucleic acid; VL = viral load.

a. Withdrawal from study intervention (including participants meeting the stopping criteria) or study

If a participant discontinues study intervention prematurely for any reason other than withdrawal of consent before the end of the double-blind prophylactic dosing phase, a withdrawal visit should be scheduled as soon as possible after the decision for discontinuation, followed by a follow-up visit, which is preferably scheduled 13 to 17 days after the last dose study intervention intake, if the condition of participant allows.

Withdraw of consent

Status: Approved, Date: 19 July 2023

Participants who withdraw consent from the study will be offered a follow-up visit.

- b. The withdrawal visit will be performed at the site. The follow-up visit can occur at the participant's home by designated study site personnel.
- c. If multiple assessments are scheduled for the same time point, it is recommended that procedures be performed in the following sequence: 12-lead ECGs, vital signs, blood draw. Parallel (central and local lab analysis) testing is allowed at the discretion of the local PI and Sponsor.
- d. Safety assessments and safety lab tests at the follow-up visit will be performed at the discretion of the investigator. If safety assessments are not required, follow-up visits can occur remotely.
- e. Throughout the study from signing of the ICF (for both AEs and concomitant therapy) until the last study-related activity, or until the participant has been deemed lost to follow-up after demonstration of due diligence of follow-up efforts.
- f. In addition to the urine pregnancy test on the withdrawal visit, an additional serum or urine pregnancy test may also be performed during the follow-up visit, as determined necessary by the investigator or required by local regulation, to establish the absence of pregnancy at any time during the participation in the study.

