7. DISCONTINUATION OF STUDY INTERVENTION AND PARTICIPANT DISCONTINUATION/WITHDRAWAL

7.1. Participant Discontinuation Criteria

A participant's study intervention must be discontinued if:

- The participant withdraws consent to receive study intervention.
- The investigator believes that for safety reasons or tolerability reasons (eg, AE) it is in the best interest of the participant to discontinue study intervention.
- The participant becomes pregnant.
- As baseline (Day 1) laboratory results will not be available at randomization, any participant who reports with 2 or more ≥ Grade 2 laboratory abnormalities for ALT, AST, creatinine, lipase, absolute neutrophil count, platelet count, or hemoglobin at baseline, must be discontinued. Discontinuation of study intervention should only occur after a confirmatory retesting result and if deemed clinically significant by the investigator.

- Noncompliance with study intervention administration occurs, defined as missing a LD, 2 consecutive MDs, or 2 nonconsecutive MDs within a week (judged case-by-case after discussion between the Sponsor and investigator).
- In case of abnormal liver tests as outlined in 10.11 Appendix 11: Liver Safety: Suggested Actions and Follow-up Assessments and Section 7.1.2 Participant Stopping Criteria due to Liver Chemistry.

If a participant discontinues study intervention prematurely for any reason other than withdrawal of consent before the end of the double-blind prophylactic dosing phase, a withdrawal visit should be scheduled as soon as possible after the decision for discontinuation, followed by a follow-up visit, which is preferably scheduled 13 to 17 days after the last dose study intervention intake, if the condition of participant allows (see Section 1.3.2.4, Discontinuation From Study Intervention or Study). Blood sample should be collected at the withdrawal and follow-up visits for immune assessments, viral analysis, viral genome sequencing, and safety assessments (at the follow-up visit, safety assessments should occur at the discretion of the investigator).

Study intervention assigned to the participant who discontinued study intervention may not be assigned to another participant. Additional participants will be entered to ensure the protocol-specified number of participants complete the study.

Please refer to Appendix 4: COVID-19 Appendix for guidance on study conduct during the COVID-19 pandemic.

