5.7. Other Analyses

5.7.1. Pharmacokinetics

All HHCs who received at least 1 dose of study drug and have at least 1 plasma concentration value after administration will be included in the analysis. Individual JNJ-64281802 plasma concentrations will be listed and summarized with descriptive statistics (n, mean, SD, geometric mean, median, minimum, maximum and interquartile ranges) by dose. Individual and summarized plasma concentration results may be graphically presented by dose and at selected time points. In this graphical presentation, special attention will be given to plasma concentration profiles of HHCs who have a lab-confirmed DENV infection between baseline and the last day of dosing + 1 day. Special attention to plasma concentration-time profiles may also be given to individuals with SAEs.

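### The SAP visit windows have no place for early-stop visits, so some concentrations drawn 13–17 days after the last dose can enter the Day 21 and Day 28 PK rows

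*SAP*

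**What the plan says.** SAP 5.1.2 states that "the following rules are applied to assign actual visits to analysis visits", and the anchor is fixed: "The reference day is the date of first study intervention intake". Relative day is visit date minus reference date plus 1 "for visits on or after Day 1". If two visits share a window, "the visit closest to the target day will be used as the protocol visit for that visit window". No rule uses the date of last dose, and Table 2 has no withdrawal or post-stop row. Its PK windows include Day 21 (Days 20–22) and Day 28 (Days 27–29). Days 15–19, 23–26 and 30–37 are Unscheduled.

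Protocol 1.3.2.4 and 7.1 give a participant who stops early, other than by withdrawing consent, a withdrawal visit "followed by a follow-up visit, which is preferably scheduled 13 to 17 days after the last dose study intervention intake". The 1.3.2.4 schedule marks "Blood sample collection for PK" at both visits.

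SAP 5.7.1 says that household contacts with at least one dose who "have at least 1 plasma concentration value after administration will be included in the analysis". Concentrations are listed and summarised by dose. The section sets no condition on whether the participant was still taking drug.

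**The concern.** A Day 21 or Day 28 row is naturally read as the concentration reached after three or four weeks of dosing. Under the rules as written, that row can also hold values from people who stopped about two weeks earlier. Such values lower the mean and geometric mean and widen the SD, so exposure looks lower and more variable than it was under dosing.

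The by-visit table carries more weight than it was designed to. After the early termination, SAP 1.1 reduces the PK endpoint to observed concentrations over time. SAP Appendix 2 limits PK to descriptive statistics and drops PK/PD, so the analyses in this SAP include no model that would account for each person's dosing history.

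**Working it through.** The plan states no figure to reproduce. The check is day arithmetic followed by a simple PK calculation.

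**1. Which samples land where.** Let L be the study day of the last dose (1–27 for an early stop) and k the offset to the follow-up visit (13–17 days). The relative day of the visit is L + k. As a check on the convention, SAP Table 1 uses first intake + 49 days for a missing Day 50 visit, and 49 + 1 = 50. There are 27 × 5 = 135 combinations. Against the PK windows they fall as follows:

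| PK row | Combinations | Last dose |
|---|---|---|
| Day 13 | 1 (1%) | Day 1 |
| Day 21 | 15 (11%) | Days 3–9 |
| Day 28 | 15 (11%) | Days 10–16 |
| Day 40 | 22 (16%) | Days 21–27 |
| Unscheduled | 82 (61%) | Days 1–27 |

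For example, with a last dose on Day 7, a sample 13–15 days later falls on Day 20–22 and is labelled Day 21. At 16–17 days it falls on Day 23–24 and is Unscheduled. The closest-to-target rule gives little protection, because the early-stop schedule lists only the withdrawal and follow-up visits; usually no on-drug sample competes for the window.

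**2. How low such a sample is.** The doses are those in protocol 4.1: HDR 400 mg loading and 150 mg maintenance, LDR 150 mg and 50 mg. The half-lives are 6.3 and 9.2 days (protocol 2.2) and about 10 days (SAP 5.1.1). The model superposes loading doses at 0, 12, 24 and 36 hours and daily maintenance from Day 3, with first-order elimination. The ratio r is the off-drug concentration divided by the predose value on the target day under full dosing.

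- Day 28 row: r = 0.18–0.41 (HDR), 0.18–0.42 (LDR).
- Day 21 row: r = 0.18–0.39 (HDR), 0.19–0.40 (LDR).

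**3. Effect on the Day 28 summary.** Let e be the proportion who stop early and attend the follow-up visit. The documents do not give e. The nearest figure is the 20% unevaluable (drop-outs and missing data) hypothesised in SAP 3, so 10% and 20% are used. Weight all 135 combinations equally, and assume that everyone else gives one on-drug Day 28 sample. The off-drug share is x = e(15/135) / [(1 − e) + e(15/135)].

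- e = 10%: x = 0.0111 / 0.9111 = 1.2%.
- e = 20%: x = 0.0222 / 0.8222 = 2.7%.

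The arithmetic mean falls by x(1 − r) and the geometric mean by 1 − r^x. With r from 0.42 to 0.18:

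| e | x | Fall in mean | Fall in geometric mean |
|---|---|---|---|
| 10% | 1.2% | 0.7–1.0% | 1.1–2.1% |
| 20% | 2.7% | 1.6–2.2% | 2.3–4.5% |

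**4. Direction of the SD.** For small x, mixing in values scaled by r raises the SD when CV² < (1 − r)/(1 + r). At the least favourable values (r = 0.42, and CV 58%, the top of the range in protocol 2.2), 0.58² = 0.34 is below 0.58/1.42 = 0.41. The SD therefore rises across the stated CV range.

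**The case against.** The strongest reply is that this is a small effect on a descriptive table. Most early-stop follow-up samples never reach the Day 21 or Day 28 row, individual concentrations are also listed, and no efficacy conclusion depends on these rows. All of that stands, and it limits the size of the point. It does not remove the point, because nothing in the SAP keeps the affected samples out.

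SAP 5.1.1 also says openly that its Prophylactic Dosing phase runs to Day 50 because of the long half-life. That phase is defined for the safety evaluation. It explains a phase label, but not why concentrations from people two weeks off drug should share a PK visit row with people still dosing.

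Four stronger readings are tempting, and the documents do not support them.

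- **A large bias.** For 5% or 10% of Day 28 samples to be off drug, about 32% or 50% of participants would have to stop early and attend, on the same equal weighting. At 10% contamination the geometric mean would fall 8–16%, but nothing in the documents points to such a rate.
- **The reported minimum must be an off-drug value.** Protocol 2.2 gives an intersubject CV of up to 58%. In a simulation with lognormal exposure at that CV, 200 on-drug samples (assumed) and one off-drug sample, the off-drug value was the minimum in 67% of runs at r = 0.18 and 14% at r = 0.42.
- **The Day 28 laboratory, vital-sign and ECG summaries need the same cut.** Post-stop results can enter that window (Days 27–34; last dose Day 10–21), but those tests are discretionary at the early-stop follow-up visit, and the extended safety phase is deliberate. A limit of last dose + 1 day would also drop completers assessed on Days 30–34. These parameters have no Day 21 window.
- **The ECG gap distorts results.** Days 16–26 have no ECG window in Table 2. By-visit ECG statistics use scheduled time points only, and the abnormality listing already covers unscheduled ones, so no by-visit result changes.

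**Conclusion.** The gap is real and confined to the by-visit PK summary. As written, SAP 5.1.2 and 5.7.1 allow concentrations taken 13–17 days after an early stop to be summarised as Day 21 or Day 28, at about 18–42% of the value expected under full dosing. The likely effect on the Day 28 row is small: a fall of about 1–2% in the arithmetic mean and 1–5% in the geometric mean, with a somewhat larger SD.

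These sizes rest on linear one-compartment kinetics, an early-stop rate of 10–20% with attendance at the follow-up visit, and an even spread of stop days and offsets. None of the last three is given in the documents. The separate data presentation specifications were not available and could contain a further rule. The primary and key secondary endpoints end at the last day of dosing + 1 day and are not affected.

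**What to change.** In SAP 5.7.1, restrict the Day 3 to Day 28 by-visit concentration statistics to samples taken up to the last day of dosing + 1 day, the limit that the SAP already uses for efficacy. In Table 2, add a Post-discontinuation analysis visit for PK and report early stoppers' later samples there. Withdrawal-visit samples within the limit stay in their day window. Leave the Day 28 laboratory, vital-sign and ECG windows as they are. As an optional tidy-up, extend the ECG Unscheduled window from Days 6–15 to Days 6–26.

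The cost is a few lines of SAP text and one derivation from the last-dose date, which SAP 5.6.1 already uses for exposure. The Day 21 and Day 28 PK rows will hold slightly fewer samples.
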